**7. Communication and dissemination of information**

If any accidental dissemination of PHI occurs, the independent monitor, [name], will communicate with the IRB immediately.

## **7.2 Auditing and Inspecting**

The Investigator will permit study-related monitoring, audits, and inspections by the IRB, government funding and regulatory bodies, and NYULMC compliance and quality assurance groups of all study related documents (e.g. source documents, regulatory documents, data collection instruments, study data etc.). The investigator will ensure the capability for inspections of applicable study-related facilities (e.g. pharmacy, diagnostic laboratory, etc.).

Participation as an investigator in this study implies acceptance of potential inspection by government regulatory authorities and applicable NYULMC compliance and quality assurance offices.

## **8 Ethical Considerations**

This study is to be conducted accordance with applicable: US government regulations, international standards of Good Clinical Practice, and institutional research policies and procedures.

This protocol and any amendments will be submitted to a properly constituted Institutional Review Board (IRB) in agreement with local legal prescriptions, for formal approval of the study conduct. The decision of the IRB concerning the conduct of the study will be made in writing to the investigator and a copy of this decision will be provided to the sponsor before commencement of this study. The investigator should provide a list of IRB members and their affiliate to the sponsor.

CONFIDENTIAL

This document and information is the property of the NYU School of Medicine and Langone Medical Center. Do not disclose or use except as authorized in writing by the study IND sponsor

All subjects for this study will be provided a consent form describing this study and providing sufficient information for subjects to make an informed decision about their participation in this study. Assent will not be required since all of the children in this study will be cognitively impaired. All consent will be coming from their legal guardians/parents/health care proxy. A consent form will be submitted with the protocol for review and approval by the IRB for the study. The formal consent of a subject, using the IRB/EC-approved consent form, must be obtained before that subject undergoes any study procedure. The consent form must be signed by the subject or legally acceptable surrogate, and the investigator-designated research professional obtaining the consent.

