#### **4.3 Subject Recruitment, Screening, and Consenting**

All patients will be recruited, consented and enrolled at the NYU Comprehensive Epilepsy Center (CEC). The NYU CEC is the ideal centers for recruitment since they already has a high influx of epilepsy patients that concomitantly have TSC or FCD. All eligible subjects have treatment resistant epilepsy with TSC or FCD and are planning to have their surgery in the next few months. All patients who are identified as potential candidates for the study will be entered into a study screening log which will document the individual who referred the subject to the study or if they were self-referred and if the subject/parents/guardian did not participate why they declined or were not eligible, and for those who were ineligible, the specific reason why they were ineligible.

The physician will explain the study during the routine visit and inform the subject and surrogate that a capacity assessment will be performed to determine whether the subject is capable of providing an informed decision to participate in the study. At this time, a capacity assessment will be conducted if the subject does not refuse the assessment. If there is already documentation of lack of capacity, no assessment will be needed. Patients who are eligible and are lacking in capacity will be allowed to participate by receiving consent from a parent/legal guardian/health care proxy. This protocol is

CONFIDENTIAL

This document and information is the property of the NYU School of Medicine and Langone Medical Center. Do not disclose or use except as authorized in writing by the study IND sponsor

specifically for patients with drug resistant epilepsy. If we were to only include patients with drug resistant epilepsy who have capacity to consent, we would have very few participants in this study, as one of the common co-morbidities of drug resistant epilepsy is global impairment.

. If the subject/parent/legal guardian/health care proxy agrees, they will be given the informed consent document and study personnel will be present to explain the study in further details the objectives and study procedures, risks and benefits. We will review the consent form documents with them and answer any questions they have. They will be given an opportunity to ask questions regarding the study and consent form. After all parties have signed off on the consent, we will give them a copy of the informed consent documents.

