#### *Consent by subject*

If the subject is 18 years old and it has been determined that he/she has capacity, he/she will review and sign an informed consent. The study personnel will be present to explain the study in further details and answer questions as needed. After all parties have signed off on consent, a copy of the informed consent documents will be given to the subject.

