#### *Assent by subject*

If the subject is 7-17 years old and it has been determined that he/she has capacity, he/she will review and sign an assent form. In addition, if the parent/legal guardian/health care proxy agrees, they will be given the informed consent document and study personnel will be present to explain in further details the study the objectives and study procedures, risks and benefits. After all parties have signed off on assent and consent, a copy of the informed assent and consent documents will be given to the subject and the subject's parent/legal guardian/health care proxy.

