#### *Consent by surrogate (for subjects lacking capacity)*

If the subject assents, and the parent/legally authorized representative agrees, they will be given the informed consent document and study personnel will be present to explain in further details the study the objectives and study procedures, risks and benefits. Legally authorized representative will be identified as per New York state law. The consent form will be reviewed and any questions they may have regarding the study and consent form will be answered. After all parties have signed off on the consent, a copy of the informed consent documents will be given to them.

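### Section 8 waives assent for every child, contradicting section 4.3, so minors with capacity could be given everolimus without their assent

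*Combined protocol and SAP*

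**What the plan says.** Section 8 gives a blanket rule and its reason: "Assent will not be required since all of the children in this study will be cognitively impaired". It continues: "All consent will be coming from their legal guardians/parents/health care proxy". The same paragraph then says: "The consent form must be signed by the subject or legally acceptable surrogate".

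Section 4.3 (Subject Recruitment, Screening, and Consenting) sets out the procedure. The physician announces the first step in these terms: "a capacity assessment will be performed to determine whether the subject is capable of providing an informed decision to participate in the study". The assessment is skipped only if the subject refuses it or lack of capacity is already documented. The Assessment subsection gives the task to a neurologist independent of the study and, for verbal long-distance children, lists four abilities to be judged. Three rules follow:

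- The subsection Assent by subject has this rule: "If the subject is 7-17 years old and it has been determined that he/she has capacity, he/she will review and sign an assent form".
- The subsection Consent by subject has this rule: "If the subject is 18 years old and it has been determined that he/she has capacity, he/she will review and sign an informed consent".
- Where capacity is lacking, the subsection Consent by surrogate has this rule: "If the subject assents, and the parent/legally authorized representative agrees, they will be given the informed consent document".

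**The concern.** Two current sections of one protocol give opposite instructions on whether a child must agree to take part, and nothing says which prevails. Section 8 is a natural place for an ethics board or a coordinator to look for the assent rule, and it says that none is needed.

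The decision is a substantial one. Section 5.3.1.5 describes everolimus as having immunosuppressive properties. Section 1.4 says that the surgical risk of this pre-operative course has never been documented. Under section 5.4 (Method for Assigning Subjects to Treatment Groups) there is no randomisation: the patient chooses between the intervention and the control group. The protocol therefore needs one clear rule on whose agreement is required.

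**Working it through.** No arithmetic applies and the plan gives no figure to reproduce. The check compares the two sections for each kind of subject.

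| Subject | Section 4.3 | Section 8 | Result |
|---|---|---|---|
| Aged 7-17, with capacity | Signs an assent form; parent or guardian consents | No assent | Direct contradiction |
| Child lacking capacity | Surrogate route starts from the subject's assent | No assent | Contradiction as worded |
| Adult with capacity | Signs own consent | Sentence on guardians is unclear; later sentence lets the subject sign | Ambiguous |
| Adult lacking capacity | Surrogate, with the subject's assent | Surrogate may sign | Consent compatible; section 8 gives no assent rule for adults |

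**Is the premise of section 8 supported?** Three places bear on it.

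1. Section 4.1 admits patients aged 2 to 50 with treatment-resistant epilepsy and TSC or FCD. Neither it nor section 4.1.1 (comparison group) requires cognitive impairment.
2. Section 4.3 explains that enrolling only people with capacity would leave very few participants, and it calls global impairment a common co-morbidity. That points to few subjects with capacity, not to none. The passage covers subjects of all ages, so it gives no count for minors.
3. Section 7.1 (Data Safety Monitor Details) expects some adults who can report side effects themselves. This shows that the population is mixed, though it says nothing about children.

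**Does the contradiction depend on the premise?** Not entirely. Suppose every child did lack capacity. Section 4.3 would still begin the surrogate route with "If the subject assents, and the parent/legally authorized representative agrees", while section 8 would still waive assent. The practical harm, a capable minor enrolled without assent, does need at least one minor with capacity.

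**Does section 4.3 work as the single rule?** Nearly. Its adult rule names age 18 exactly, although eligibility runs to 50. Its surrogate rule, read literally, depends on assent from people who may be unable to give it: patients can be as young as 2, and nonverbal long-distance children are deemed to lack capacity. Nothing says what happens then.

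**The case against.** Section 4.3 is the detailed operating procedure, with its own assessor, and all patients are consented at one centre. Staff who follow it will seek assent as intended, so harm arises only if the general paragraph is followed instead. That stands, and it limits the urgency. It does not remove a contradictory instruction.

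Four stronger readings are tempting, and the documents do not support them:

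- **Section 8 removes consent from capable adults.** A reader might infer this from "All consent will be coming from their legal guardians/parents/health care proxy". But that sentence directly follows one about the children, so it most naturally refers to them. The same paragraph lets the subject sign, and section 4.3 has subjects with capacity consent for themselves. The wording is ambiguous for adults and no more than that.
- **A consent or assent breach would cost primary-endpoint data and power.** No passage makes tissue or data unusable after such a deviation. Subject Population(s) for Analysis includes patients who undergo surgery in the S6 analysis, and Visit 5a provides for sample destruction when a subject withdraws in writing. Losing subjects from a treated arm of 9 would matter, but nothing here shows that any would be lost.
- **Providing for a capacity assessment proves that some children have capacity.** It does not, since an assessment can find none. The support is section 4.3's remark about very few participants, which also suggests that few subjects are exposed.
- **Section 8 narrows eligibility.** It makes a poorly supported prediction about the children enrolled and sets no entry criterion.

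**Conclusion.** The point holds for minors' assent. Section 8 waives assent outright, while section 4.3 requires it from 7-17-year-olds with capacity and makes it the first step of the surrogate route. The reason given in section 8 is not supported by the eligibility criteria or by section 4.3's own account of the population. If section 8 governed, a capable minor could receive everolimus before elective surgery without having agreed.

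The number of minors affected cannot be stated, because the documents do not give the share with capacity; section 4.3 suggests that it is small. The practical consequence assumes that at least one enrolled minor has capacity and that staff act on section 8 instead of section 4.3. For adults the finding is limited to one ambiguous sentence. It is a matter of subject protection, with no demonstrated effect on sample size, power or the S6 comparison. It should be corrected because the text is wrong and the correction is small.

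**What to change.** In section 8, delete the sentence waiving assent and the sentence on all consent coming from guardians. Replace them with:

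> Consent and assent follow section 4.3: assent is sought from every subject aged 7-17 found to have capacity, and subjects aged 18 or older with capacity consent for themselves.

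Then align section 4.3:

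- Under Consent by subject, change the age wording to 18 years or older.
- Under Consent by surrogate, reconcile the opening condition with subjects who cannot assent, such as very young or nonverbal children, and state how they are handled.

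The cost is two sentences in section 8 and two edits in section 4.3. The capacity assessor and an assent form are already named there. Section 8 mentions only a consent form for submission to the ethics board, so confirm that the assent form is submitted as well. The downside is that a few capable subjects may decline, in a study whose summary already reports difficult recruitment.

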## **9 Study Finances**

### **9.1 Funding Source**

The collection of preliminary data for this study at NYU Langone Medical Center will be funded through a grant from Novartis. Study drug and funding will be supplied by Novartis For the randomized study, funding will be requested from the National Institutes of Health using an RO1 grant application.

### **9.2 Conflict of Interest**

Any investigator who has a conflict of interest with this study (patent ownership, royalties, or financial gain greater than the minimum allowable by their institution, etc.) must report this to the study IND Sponsor and have the conflict reviewed by a properly constituted Conflict of Interest Committee with a Committee-sanctioned conflict management plan that has been reviewed and approved by the study sponsor prior to participation in this study. All NYULMCinvestigators will follow the applicable University conflict of interest policies.

### **9.3 Subject Stipends or Payments**

Subjects will not be compensated for travel for any study-related expenses.

## **10 Publication Plan**

Neither the complete nor any part of the results of the study carried out under this protocol, nor any of the information provided by the sponsor for the purposes of performing the study, will be published or passed on to any third party without the consent of the study sponsor.

